## 4.1.5. Cycle Length and Duration

Cycle 1 Day 1 is the day that the first dose of study drug is administered. Part 1 of the study will begin with 14-day cycles; however, alternate dose schedules may also be explored depending on PK,

One treatment cycle consists of 14 days (or 21, or 28 days if the alternative schedule is tested). The first cycle of therapy is defined as the period beginning with the first dose of INCAGN01876 and ending the earlier of the following: 1) 14 calendar days (inclusive) later, or 21 calendar days (inclusive) later, or 28 calendar days (inclusive) later, if the alternative schedule

is tested; or 2) permanent discontinuation of INCAGN01876. Subsequent cycles have Day 1 as the corresponding visit date associated with the corresponding cycle.

In Part 2, subjects will be administered study drug at the RP2D and schedule. Subjects will continue to receive INCAGN01876, up to the defined maximum number of cycles, as long as the subject is deriving benefit and has not met any of the Protocol-defined conditions for treatment withdrawal.

Duration of treatment (maximum number of cycles) will be determined based on safety during Part 1 and may be fewer than the absolute maximum number of cycles as outlined below:

• For a 14-day cycle: maximum of 26 cycles

• For a 21-day cycle: maximum of 17 cycles

• For a 28-day cycle: maximum of 13 cycles

#### 4.2. Variable Definitions

#### 4.2.1. Derived Variables

The following variable is provided on the CRF but also derived for analysis purposes. The MSKCC (Motzer et al 2004) criteria will be summarized for both investigator reported and derived data for RCC subjects.

## 4.2.1.1. MSKCC Criteria for Renal Cell Carcinoma Subjects

The MSKCC (Motzer et al 2004) score will be derived as a prognostic tool for RCC subjects enrolled in Parts 1 and 2. The calculation for the MSKCC score is provided below as the sum of 5 component "no" vs "yes" (0 vs 1) scores. For each component, subjects will have a score of 1 for each criterion they meet. An MSKCC total score of 0 indicates a prognosis of Good. A MSKCC total score of 1 to 2 indicates an Intermediate prognosis, and a total score of  $\geq$  3 indicates a Poor prognosis. The derivation of MSKCC will use screening data; if screening data is not available, then Cycle 1 Day 1 data will be used.

- 1. Time from diagnosis to systematic treatment < 1 year
- 2. Low hemoglobin
  - Men (normal): 13.5 to 17.5 g/dL
  - Women (normal): 12.0 to 15.5 g/dL
- 3. Calcium > 10 mg/dL (> 2.5 mmol/L)
- 4. Lactate dehydrogenase > 420 U/L
- 5. Performance status: Karnofsky < 80% or ECOG > 1

Missing dates for time of first systemic treatment will be handled according to rules for missing partial disease/cancer diagnosis date that are given in Section 4.1.4.

#### 4.2.1.2. Prior and Concomitant Medication

Prior medication is defined as any nonstudy medication started before the first dose of INCAGN01876.

Concomitant medication is defined as any nonstudy medication that is started accordingly:

- Before the date of first administration of INCAGN01876 and is ongoing throughout the study or ends on/after the date of first study drug administration.
- On/after the date of first administration of INCAGN01876 and is ongoing or ends during the course of study drug.

A prior medication could also be classified as "both prior and concomitant medication" if the end date is on or after first dose of INCAGN01876. In the listing, it will be indicated whether a medication is prior-only, concomitant-only, or both prior and concomitant medication.

For the purposes of analysis, all medications will be considered concomitant medications unless the medications can unequivocally be defined as not concomitant.

## 4.2.2. Variables to Be Derived Only If Not Provided on Case Report Form

The following variables will only be calculated if not reported on the CRF.

• Subject age will be calculated as the integer part of the number of years from date of birth to the date of signing the informed consent form, using the following formula:

Age = integer part of (date of informed consent – date of birth + 1) / 365.25

## 5. STATISTICAL METHODOLOGY

## 5.1. General Methodology

Unless otherwise noted, SAS® software (SAS Institute Inc, Cary, NC; Version 9 or later) will be used for the generation of all tables, graphs, and statistical analyses. Descriptive summaries for continuous variables will include, but not be limited to, the number of observations, mean, standard deviation, median, minimum, and maximum. Descriptive summaries for categorical variables will include the number and percentage of subjects in each category.

Interim analyses are planned for this study as defined in Section 9.

# **5.2.** Treatment Groups

This is a Phase 1/2, open-label, nonrandomized, multicenter, dose-escalation study. Up to 8 doses will be tested. Data will be summarized overall and by treatment group. Treatment group is defined as the dose regimen initially assigned. Treatment cycles will begin Q14D (± 3 days), but alternate dose schedules (Q21D and/or Q28D) may also be explored due to emerging safety, PK,

- 0.01 mg/kg Q14D
- 0.03 mg/kg Q14D

- 0.1 mg/kg Q14D
- 0.3 mg/kg Q14D
- 1 mg/kg Q14D
- 3 mg/kg Q14D
- 5 mg/kg Q14D
- 10 mg/kg Q14D

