5.4. Treatment Interruptions and Adjustments

5.4.1. Dose Modifications

Selections and modifications to the study drug are planned for dose-escalation cohorts. Dose interruptions and modifications also may occur for individual study subjects. The identification of DLTs will define the doses used in planned cohorts (see [Section 5.4.2](#)). Further, the occurrence of DLTs and other toxicities (related or unrelated to study drug) will guide decisions for treatment interruptions and discontinuation for individual subjects. Intrasubject dose escalation is not permitted; however, once the RP2D has been determined, ongoing subjects in Part 1 may be permitted to dose escalate to the RP2D with medical monitor approval.

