beginning with Cohort 1 (0.03 mg/kg; starting dose). There will be a waiting period of 48 hours between dose administration of the first subject and second subject of each dose cohort. The first 3 subjects enrolled within a cohort will be observed for a DLT observation period of 28 days before the next cohort begins enrollment. The dose will be escalated if 0 of the first 3 evaluable subjects enrolled has a DLT. If 1 of the first 3 evaluable subjects enrolled has a DLT, then the cohort will be expanded to include 3 additional evaluable subjects, and if no DLT occurs in the additional 3 subjects, then the dose will be escalated. If a DLT occurs in one-third or more of the expanded cohort, then the MTD will be deemed to be exceeded, and the prior dose level will be considered the MTD. If only 3 subjects were treated at the MTD or PAD, then a minimum of 3 additional subjects will be enrolled before this dose is administered in Part 2 of the study.

If Cohort 1 (0.03 mg/kg; starting dose) exceeds the MTD, the sponsor and investigators will consider dosing INCAGN01876 at 0.01 mg/kg (Cohort -1), and/or investigate 0.03 mg/kg at alternate dose schedules, based on available safety, PK, data. If an alternate schedule is tested and determined to be safe, re-escalation of INCAGN01876 will proceed according to Table 1.

Throughout the treatment period, if > 33% of subjects (a minimum of 6 subjects) experience a  $\ge$  Grade 3 toxicity related to study drug after completing  $\ge$  4 cycles, then dose administration will be stopped, and the MNTD will be determined in conjunction with the investigators and sponsor based on all available safety data.

[figure not shown]
Additional subjects will be enrolled in a cohort to achieve the minimum of 3 evaluable subjects. Subjects who drop out for reasons other than a DLT (eg, events clearly associated with the underlying disease, disease progression, concomitant medication, or comorbidity) during the 28-day DLT observation period will be considered nonevaluable and will be replaced. Dose modifications should not be made during the DLT observation period without discussion with the medical monitor. Intrasubject dose escalation is not permitted; however, once the RP2D and schedule has been determined, ongoing subjects in Part 1 may be permitted to escalate to the RP2D with approval of the medical monitor. The cohorts and dose levels are shown in Table 1.

| Table 1. | INCAGN01876 Dose I    | l ovole and | Caharte |

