# 6. BASELINE, EXPOSURE, AND DISPOSITION VARIABLES AND ANALYSES

Appendix A provides a list of data displays and sample data displays.

# 6.1. Baseline and Demographics, Physical Characteristics, and Disease History

## 6.1.1. Demographics

The following demographics will be summarized for the Part 1 FAS population by dose level and for the Part 2 FAS population by tumor type: age, sex, race, ethnicity, and ECOG performance status.

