### 7.4.2. Objective Response Rates and Best Overall Response

A subject is defined as an objective responder if the subject has an overall response of CR or PR at any postbaseline visit before first PD. Objective responders will be assessed based on both RECIST v1.1 and mRECIST v1.1.

Objective response rate is defined as the proportion of subjects with objective responses. Objective response rate will be estimated with 95% CIs overall by cohort-specific tumor type. Confidence intervals will be calculated based on the method for Simon 2-stage CIs of response rates outlined in Koyama and Chen (Koyama and Chen 2008). Subjects who do not have sufficient baseline or on-study response assessment information to be adequately assessed for response status will be included in the denominators in the calculation of ORR.

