#### 8.1. General Considerations

Summary tables may be replaced with listings when appropriate. For instance, an AE frequency table may be replaced with a listing if it only contains a few unique PTs reported on relatively few subjects. Data from the Part 1 portion will be summarized separately where appropriate. Additional summaries for specific subgroups may be included on an ad hoc basis.

Unless otherwise stated, table summaries will be limited to AEs occurring within 60 days of the last administration of study drug.

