#### **8.2.5.** Adverse Event Summaries

An overall summary of AEs by treatment group and by tumor type as applicable will include the following:

- Number (%) of subjects reporting any TEAEs
- Number (%) of subjects reporting any DLTs
- Number (%) of subjects reporting any SAEs
- Number (%) of subjects reporting any Grade 3 or higher TEAEs
- Number (%) of subjects reporting any TEAEs related to INCAGN01876
- Number (%) of subjects who dose interrupted INCAGN01876 because of TEAEs
- Number (%) of subjects who permanently discontinued INCAGN01876 because of TEAEs
- Number (%) of subjects with INCAGN01876 dose reductions because of TEAEs
- Number (%) of subjects who had a fatal TEAE
- Number (%) of subjects who withdrew from study because of an TEAE

The following summaries will be produced by MedDRA term (if 10 or fewer subjects appear in a table, a listing may be appropriate):

- Summary of TEAEs by SOC and PT
- Summary of TEAEs by PT in decreasing order of frequency
- Summary of TEAEs by SOC, PT, and highest CTCAE grade/maximum severity
- Summary of Grade 3 or higher TEAEs by SOC and PT
- Summary of INCAGN01876 treatment-related AEs by SOC and PT
- Summary of Grade 3 or higher INCAGN01876 treatment-related AEs by SOC and PT
- Summary of all TEAEs, treatment-related AEs, Grade 3 or 4 TEAEs, and treatment-related Grade 3 or 4 TEAEs.
- Summary of INCAGN01876 treatment-related AEs by SOC, PT, and highest CTCAE grade/maximum severity
- Summary of TEAEs leading to death by SOC and PT
- Summary of treatment-emergent SAEs by SOC and PT
- Summary of treatment-emergent SAEs by PT in descending order of frequency
- Summary of INCAGN01876 treatment-related SAEs by SOC and PT
- Summary of TEAEs leading to INCAGN01876 dose reduction by SOC and PT
- Summary of TEAEs leading to INCAGN01876 dose interruption by SOC and PT
- Summary of TEAEs leading to discontinuation of INCAGN01876 by SOC and PT
- Summary of treatment-emergent non-SAE by SOC and PT.

- Summary of irAEs by SOC and PT.
- Summary of Grade 3 or higher irAEs by SOC and PT.
- Number (%) of subjects reporting an immune-related AE (irAE)
- Number (%) of subjects reporting any Grade 3 or 4 irAE
- Number (%) of subjects reporting an immune-related treatment-related AE (irAE)
- Number (%) of subjects reporting an immune-related treatment-related Grade 3 or 4 AE (irAE)

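### Part 1 dose-level safety and efficacy tables group subjects by starting dose, with no rule for data collected after escalation to the RP2D

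*SAP*

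**What the plan says.** SAP 5.2 sets the general display rule, "Data will be summarized overall and by treatment group", and then fixes the group: "Treatment group is defined as the dose regimen initially assigned". SAP 8.2.5 applies it to safety: "An overall summary of AEs by treatment group and by tumor type as applicable will include the following". Baseline data are shown "for the Part 1 FAS population by dose level and for the Part 2 FAS population by tumor type" (SAP 6.1.1). The Part 1 shells in SAP Appendix A for adverse events (Tables 3.2.1.1 onward), laboratory shifts (3.3.2.1, 3.3.4.1), response (2.1.1, 2.2.1) and PFS (2.3.1, 2.4.1) are likewise laid out by dose level.

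Dose can change upward within a subject. Once the RP2D and schedule are set, SAP 3.1.1 says that "ongoing subjects in Part 1 may be permitted to escalate to the RP2D with approval of the medical monitor". Protocol 5.4.1 gives the same permission: "ongoing subjects in Part 1 may be permitted to dose escalate to the RP2D with medical monitor approval".

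The analysis windows do not stop at such a change. Under SAP 8.1, "table summaries will be limited to AEs occurring within 60 days of the last administration of study drug". Under SAP 7.4.2 a responder is a subject with "an overall response of CR or PR at any postbaseline visit before first PD". SAP 8.2.1 reports only the worst grade of an event, and SAP 8.3.2 takes the worst postbaseline laboratory grade.

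**The concern.** A subject who starts at a low dose and later receives the RP2D contributes two kinds of follow-up, but only one label. A Grade 3 event or a first partial response that appears under the RP2D is printed in the low-dose column. The worst-grade rule sharpens this: a Grade 1 event at the starting dose that recurs as Grade 3 after escalation is shown once, as Grade 3, under the starting dose.

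The primary endpoint is the frequency, duration and severity of adverse events, and the Part 1 dose-level tables are where a reader will look for how these vary with dose. Cohorts hold 3 to 6 evaluable subjects, so a few relabelled events can change how a column reads.

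**Working it through.** **Is there a rule that handles the change?** Taking the SAP sections in turn:

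| Item | SAP or protocol place | Basis | Affected? |
|---|---|---|---|
| Part 1 AE tables | SAP 5.2, 8.1, 8.2.5 | Starting dose; to 60 days after last dose | Yes |
| Part 1 laboratory shifts | SAP 5.2, 8.3.2 | Starting dose; worst postbaseline grade | Yes |
| Part 1 response and PFS tables | SAP 5.2, 7.4.2, 7.4.8 | Starting dose; no cut at a dose change | Yes |
| DLT and cohort decisions | Protocol 5.4.2 | Events through Day 28 | No |
| Exposure | SAP 6.4 | Actual dose per cycle | No |
| PK | SAP 7.6 | Part, dose and cycle | No |
| Part 2 tables | SAP 6.1.1, 5.3.3 | Tumor type | No, apart from the FAS question below |

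No section assigns post-escalation events to the dose at onset.

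**Size.** The plan states no figure to reproduce. It gives no number of escalating subjects and no event rates, so everything below is illustration on assumed rates.

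Let n subjects start at a lower dose, k of them escalate, qL be the risk of a Grade 3 or higher event at the starting dose and qH the further risk after escalation. The rate displayed for the lower dose is

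[(n − k) × qL + k × (1 − (1 − qL)(1 − qH))] / n.

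- With n = 6, k = 3, qL = 5%, qH = 20%: 3 × 0.05 + 3 × (1 − 0.95 × 0.80) = 0.15 + 0.72 = 0.87 expected subjects with an event, and 0.87 / 6 = 14.5%. Without post-escalation events it is 6 × 0.05 = 0.30, or 5%. The difference is 0.57 of a subject.
- Part of that difference is simply longer follow-up. If the same three had stayed at the lower dose for a second period with the same 5% risk, the display would be [0.15 + 3 × (1 − 0.95 × 0.95)] / 6 = 0.4425 / 6 = 7.4%.
- With n = 6, qL = 10% and qH from 20% to 40%, the lower dose displays as follows, against 10% when cut at escalation:

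| Escalators of 6 | Displayed rate |
|---|---|
| 1 | 13.0% to 16.0% |
| 2 | 16.0% to 22.0% |
| 3 | 19.0% to 28.0% |

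One event in a cohort of 6 is 1/6 = 16.7 points.

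For responses, take the RP2D response rate r between the null and target values of SAP 7.2, 5% and 25%. The chance that at least one response under the RP2D is printed under a lower dose is 1 − (1 − r)^k: 5% to 25% with one escalator, and 14% to 58% with three.

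**The RP2D column.** Escalated subjects are absent from both its numerator and its denominator. If the true rate is 20%, the expected rate among those who started there is still 20%. The column has fewer subjects to learn from, but it is not shifted.

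**Part 2 FAS.** SAP 5.3.3 combines eligible Part 1 subjects of the same tumor type who were treated at the MTD/PAD with the Part 2 subjects, and uses the tumor-type subgroups for the Simon rules. It does not say whether reaching that dose by escalation counts. If it does, one response could appear in a Part 1 low-dose column and again in a Simon cohort.

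**The case against.** Grouping by initial assignment is a clear, prespecified convention, and SAP 3.3 calls all analyses exploratory. Escalation is optional and needs an RP2D already chosen, a subject still on treatment and approval. With eight cohorts in the protocol, each followed for 28 days, and one further 28-day safety-expansion window, a Cohort 1 subject would wait about (8 + 1) × 4 = 36 weeks even with instant enrolment, against a cap of 26 × 14 days = 52 weeks. Three of six low-dose escalators is therefore not a typical case, though later cohorts or an early stop at a PAD shorten the wait. All of this stands, and it limits the likely size.

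Attribution by dose at onset also has a weakness. Protocol 5.4.7 says immune-related events can appear months after the last dose, so a late event may belong to the earlier dose. Cutting follow-up at escalation shortens it selectively in subjects who stayed on drug. This is a reason to keep the existing tables beside any new ones.

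Listings of dosing, adverse events and response are planned, and SAP 8.1 allows ad hoc subgroup summaries. These let a reader trace the events, but they do not correct the planned tables. The convention also suits dose reductions better: there it keeps toxicity with the dose that led to the reduction, whereas after escalation it assigns events to a dose below the one received.

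A reader might infer that every summary is affected, that the RP2D is made to look safer, or that the MTD is compromised. The documents do not support these readings. Exposure and PK carry dose detail, and Part 2 is shown by tumor type. The RP2D rate is not lowered, for the reason shown in the working. DLT decisions use events to Day 28. Protocol 5.4.2 does allow a later lowering of the MTD, and the MNTD rule uses toxicity after four or more cycles, but neither is tied to the Part 1 tables. Nor is the primary endpoint defined as a comparison by dose.

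**Conclusion.** The point holds for the Part 1 dose-level adverse event, laboratory and efficacy tables. Under the stated rule, post-escalation events and responses are counted under a lower dose than the one being received. This contaminates the lower-dose columns, toward overstated toxicity or activity, and loses information on the RP2D.

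The effect is conditional on escalation taking place. The move from 5% to 14.5% rests on assumed rates, on half of a six-subject cohort escalating, and on charging each escalator a full additional period of risk. It shows what is possible and is not an estimate. Severity is minor to moderate: no design probability or Day 28 decision changes, but the planned tables would be hard to read by dose if several subjects escalate.

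**What to change.** These changes concern analysis and display only.

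- In SAP 5.2 and 8.2.5, keep initial assignment for disposition, DLTs and the existing tables.
- For subjects who escalate, add Part 1 dose-level adverse event, laboratory and response summaries cut at the first escalated dose. Show events with later onset, and responses first seen later, in a separate column for the period after escalation to the RP2D. Do not pool that column with subjects who started at the RP2D, because escalated subjects are selected for having stayed on treatment.
- Footnote that delayed immune-related events in that column may reflect the earlier dose.
- In SAP 5.3.3, state whether a Part 1 subject who reached the MTD/PAD by escalation counts as treated at it for the Part 2 FAS, so that no response is counted in both places.

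The cost is SAP wording, a few extra shells, and cut-off versions of the worst-grade and best-response derivations. SAP 6.4 already takes the dose of each infusion from the CRF, so no new data are needed. Some ambiguity in attributing delayed events will remain.

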## 5.3. Analysis Populations

## 5.3.1. Full Analysis Set Population

The FAS population includes all subjects enrolled in the study who received at least 1 dose of INCAGN01876. The FAS population will be used for the summary of demographics, baseline characteristics, subject disposition, safety, study drug administration, and analyses of all efficacy data.

## 5.3.2. Part 1 Full Analysis Set Population

The Part 1 FAS population includes all subjects in the FAS population enrolled in Part 1 of the study who received at least 1 dose of INCAGN01876.

## 5.3.3. Part 2 Full Analysis Set Population

The Part 2 FAS population includes all subjects in the FAS population enrolled in Part 2 of the study who received at least 1 dose of the MTD/PAD of INCAGN01876. Subjects tested in the Part 1 (dose escalation and safety expansion) who are treated at the MTD/PAD and in Part 2, who are of the same tumor type, and who meet inclusion/exclusion criteria used for the tumor type of interest in Part 2 will be combined for both safety and efficacy summary purposes.

Specific analysis populations to be used for evaluating the Simon 2-stage efficacy rules include the following subgroups:

- Part 2 FAS population subjects with adenocarcinoma of endometrium
- Part 2 FAS population subjects with melanoma
- Part 2 FAS population subjects with NSCLC
- Part 2 FAS population subjects with RCC

Table summaries, unless otherwise indicated, will be provided by tumor-specific cohort.

### **5.3.4.** Per Protocol Population

Subjects in the FAS population who are considered to be sufficiently compliant with the Protocol comprise the PP population.

The following procedures will be performed to identify those subjects who are to be excluded from the PP population before the database lock:

- Clinical review of Protocol deviations/violations
- Clinical review of concomitant medications (prohibited medications) as defined in Section 5.6.3 of the Protocol.
- Clinical review of the dose administration and drug accountability listing.

## 5.3.5. Pharmacokinetic Evaluable Populations

## 5.3.5.1. Pharmacokinetic Evaluable Population

The PK evaluable population will include all subjects who received at least 1 dose of INCAGN01876 and provided at least 1 postdose sample (1 PK measurement). The study pharmacokineticist will review data listings of study drug administration and sample records to identify subjects to be excluded from analyses of PK data.

